8.8.2 Clinical laboratory evaluations

SI units will be used for all summaries and presentations (including listings) of laboratory data.

Descriptive statistics of observed values and change from baseline will be presented for clinical laboratory (hematology, biochemistry and coagulation) and continuous Urinalysis evaluations (by treatment group and visit.

Categorical urinalysis (protein and occult blood) parameters will be tabulated by visit and treatment group in frequency tables.

The clinical safety laboratory tests that will be summarized are listed below.

- a. Haematology: haemoglobin, HbA1c, haematocrit, red blood cell (RBC) count, WBC count, platelet count, mean corpuscular haemoglobin, mean corpuscular haemoglobin concentration, mean corpuscular volume, absolute basophils, absolute eosinophils, absolute lymphocytes, absolute monocytes, absolute neutrophils.
- b. Biochemistry: sodium, potassium, chloride, bicarbonate, urea (BUN), uric acid, creatinine (enzymatic), albumin, glucose, cholesterol (total cholesterol, LDL [calc and mes], HDL fractions), triglycerides, aspartate aminotransferase (AST), alanine aminotransferase (ALT), alkaline phosphatase, bone-specific alkaline phosphatase, lipase, amylase, gamma glutamyl aminotransferase (GGT), bilirubin (total, indirect, direct), lactate dehydrogenase, total protein, hs-CRP and eGFR calculation;
- c. **Coagulation**: activated partial thromboplastin time, prothrombin time, and international normalised ratio.
- d. Urine analysis: urinalysis by dipstick glucose, protein, and occult blood.

Shift tables from Baseline to the end of treatment, with regard to normal range (low, normal, high), will be presented by treatment group for each of the laboratory parameters

All laboratory and urinalysis data will be listed.

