*Actimetry is continuously recorded from Day 0 to M6.

^f Reconsent based on the COVID-19 outbreak and the next planned visit of the participant

1 Biochemistry: sodium, potassium, chloride, bicarbonate, urea, uric acid creatinine, albumin, glucose, cholesterol (total cholesterol, LDL, HDL fractions), triglycerides, aspartate aminotransferase (AST), alanine aminotransferase (ALT), alkaline phosphatase, bone-specific alkaline phosphatase, lipase, amylase, gamma glutamyl aminotransferase, bilirubin (total, indirect, direct), creatine phosphokinase and mb-creatine phosphokinase, lactate dehydrogenase, total protein, and eGFR calculation;

2 Hematology: haemoglobin, HbA1c, hematocrit, red blood cell (RBC) count, white blood cell (WBC) count with differential, platelet count, mean corpuscular haemoglobin, mean corpuscular haemoglobin concentration, mean corpuscular volume; Coagulation: activated partial thromboplastin time, prothrombin time, and international normalized ratio.

3 Urinalysis: a midstream urine sample will be collected for urinalysis by dipstick for glucose, protein, and occult blood.

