- **Biological specimen collection and laboratory evaluations:** Blood samples will be collected by venepuncture or via indwelling cannula at screening, M1, M3 and at M6 visits for biochemistry and analyses. In case of previous abnormalities or new symptoms, a blood sample can be collected at M5
 - a. **Hematology**: hemoglobin, HbA1c, hematocrit, red blood cell (RBC) count, white blood cell (WBC) count with differential, platelet count, mean corpuscular haemoglobin, mean corpuscular haemoglobin concentration, mean corpuscular volume
 - b. Biochemistry: sodium, potassium, chloride, bicarbonate, urea, uric acid creatinine, albumin, glucose, cholesterol (total cholesterol, LDL, HDL fractions), triglycerides, aspartate aminotransferase (AST), alanine aminotransferase (ALT), alkaline phosphatase, bone-specific alkaline phosphatase, lipase, amylase, gamma glutamyl aminotransferase, bilirubin (total, indirect, direct), creatine phosphokinase and mb-creatine phosphokinase, lactate dehydrogenase, total protein, and GFR estimation based on Cockroft & Gault calculation
 - c. **Coagulation**: activated partial thromboplastin time, prothrombin time, and international normalized ratio.
 - d. **Urine analysis**: A midstream urine sample will be collected for urinalysis by dipstick for glucose, protein, and occult blood

All study analyses will be performed by a centralized laboratory. The Investigator must review the laboratory report, document this review, and record any changes occurred during the study. Laboratory values outside the normal ranges will be flagged and their clinical relevance will be assessed by the Investigator. **See also Exclusion criteria based on lab results and stopping rules in Section 5.3** Exclusion criteria and temporary exclusion criteria and **Section 7.1** discontinuation of study intervention, respectively.

- **Counseling procedures, including any dietary or activity considerations**: see section 5.4 Lifestyle considerations
- Assessment of study intervention adherence: see Study Intervention Compliance, section 6.4
- Administration of the PROs: see Efficacy Assessments, Section 8.1

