9.4.5 SAFETY ANALYSES

Safety variables will be summarized/analyzed by groups of treatment, on the Safety population.

Vital signs, biochemistry and hematology parameters will be described by descriptive statistics, for the entire period of the study and at each timepoint.

Usual tables (by SOC and preferred term) will be produced for AEs (falls, injurious falls and orthostatic hypotension will be tabulated separately) after coding with the MEDRA terms.

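### SAP 8.8.2 leaves creatine phosphokinase and its MB fraction off the list of laboratory tests to be summarized, and does not declare this as a change from the protocol

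*SAP*

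**What the plan says.** The protocol gives the biochemistry panel twice. In the Schedule of Activities (section 1.3, footnote 1) it ends with "bilirubin (total, indirect, direct), creatine phosphokinase and mb-creatine phosphokinase, lactate dehydrogenase, total protein, and eGFR calculation". In section 8.2 it ends with "creatine phosphokinase and mb-creatine phosphokinase, lactate dehydrogenase, total protein, and GFR estimation based on Cockroft & Gault calculation". Section 8.2 plans blood sampling "at screening, M1, M3 and at M6 visits for biochemistry and analyses"; under the COVID-19 schedule in section 1.3, biochemistry is marked only at screening and at the end-of-intervention visit.

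On analysis, protocol 9.4.5 says safety variables are summarized by treatment group on the safety population, and then: "Vital signs, biochemistry and hematology parameters will be described by descriptive statistics, for the entire period of the study and at each timepoint". It names no exception.

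SAP 8.8.2 opens with by-group, by-visit descriptive statistics of observed values and change from baseline for hematology, biochemistry and coagulation. It then sets the scope: "The clinical safety laboratory tests that will be summarized are listed below". The biochemistry entry under that sentence contains "bilirubin (total, indirect, direct), lactate dehydrogenase, total protein, hs-CRP and eGFR calculation". The section closes with shift tables from baseline to end of treatment, which "will be presented by treatment group for each of the laboratory parameters", and with a commitment to list all laboratory data.

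**The concern.** The SAP list follows the protocol panel in the same order but goes straight from bilirubin to lactate dehydrogenase, at the point where the protocol has the two enzymes. A programmer working from the SAP would build tables for the listed tests, and these two would not be among them.

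The enzymes are relevant to this product. Protocol 2.3.2 bases the expected benefit on non-clinical effects on muscle and muscle cells. Protocol 2.2 reports musculoskeletal and connective tissue disorders among the most frequent adverse events in the single-dose part of Phase 1, where the events were mild. SAP 8.8 plans no hypothesis testing for safety, so the by-arm descriptive and shift tables are the main place where a modest group-level laboratory shift would be seen. A subject listing shows individual values but does not compare arms.

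**Working it through.** There is no sample size, power or alpha figure to reproduce. The check is an analyte-by-analyte comparison of the two lists, followed by a reading of the sentences that govern them.

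**Step 1: count the panels.** Cholesterol and bilirubin fractions are counted separately, and LDL calculated and measured are counted as one.

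- Protocol panel (1.3 footnote 1 and 8.2): 28 analytes.
- SAP 8.8.2 biochemistry list: 27 analytes.
- In the protocol but not the SAP: creatine phosphokinase and MB-creatine phosphokinase, and nothing else.
- In the SAP but not the protocol: hs-CRP, and nothing else.
- Check: 28 − 2 + 1 = 27.

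**Step 2: is the removal declared?** The SAP's section on changes to the planned analysis has five entries: the safety population definition, futility stopping at the interim analysis, the move from Month 6 to Month 6/Month 9, the missing-data sensitivity analyses, and the last assessment on treatment. None concerns laboratory tests. The first records the deletion of a single clause, so by the SAP's own practice the removal of two analytes should have an entry.

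**Step 3: what each output would contain.**

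| Output | Governing text | The two enzymes |
|---|---|---|
| By-arm, by-visit descriptive and change-from-baseline tables | SAP 8.8.2, limited by the list | Not covered if the list is followed |
| Shift tables by arm | SAP 8.8.2, "will be presented by treatment group for each of the laboratory parameters" | Ambiguous: the listed tests, or every collected test |
| Subject listings | SAP 8.8.2, all laboratory data | Covered |
| By-arm adverse event tables | Protocol 7.1 and 8.2; SAP 8.8.1 | Covered only where the investigator judges the change clinically relevant |

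**Step 4: compare with the protocol's commitment.** Protocol 9.4.5 promises a description by group and timepoint for biochemistry parameters in general. The first row of the table falls short of that for two analytes. The other rows do not replace it: a shift table compares normal-range categories between baseline and end of treatment, a listing does not summarize, and adverse event tables capture selected cases.

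**The case against.** A reader might infer that no by-arm table of these enzymes would exist at all, and that a treatment-related rise could not be seen in any by-arm output. The documents do not support that, for three reasons.

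- The shift-table sentence refers to each of the laboratory parameters and does not say that it means only those listed. It comes after the list, so the listed tests are the more natural reading, but the broader one is open.
- Protocol 8.2 has out-of-range values flagged and assessed by the investigator, protocol 7.1 has new clinically relevant findings reported as adverse events, and SAP 8.8.1 tabulates treatment-emergent events by arm. A clinically relevant elevation therefore has a by-arm route.
- The SAP's contents page shows a biomarker section under 8.7.4 that is not in the available text, and the table templates are in a separate document. A summary of the enzymes there cannot be ruled out.

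It can also be said that the SAP list is not a plain copy of the protocol panel. It adds hs-CRP and assay detail on creatinine and LDL, so it may follow what the central laboratory reported. If the enzymes were never assayed, adding them to a table would not be possible. The documents show planned collection only.

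Finally, the named events of special interest are falls, injurious falls and orthostatic hypotension, and the analyte in the protocol 7.1 stopping rule is blacked out. No link between that rule and these enzymes can be drawn.

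These points limit the consequence and make the remedy conditional. They leave standing that the list omits two protocol analytes, that protocol 9.4.5 promises to describe them, and that the SAP does not declare the change. A summary elsewhere as an exploratory biomarker would not be the safety summary that protocol 9.4.5 describes.

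**Conclusion.** The omission is real and undeclared. Two of the 28 biochemistry analytes in the protocol would have no by-arm, by-visit descriptive or change-from-baseline summary in the safety laboratory tables, and their place in the shift tables is unclear. What could be missed is a sub-clinical difference between arms, in mean level or in normal-range category. Individual values and clinically relevant elevations would still be reported.

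This rests on two assumptions: that the list in SAP 8.8.2 is closed, as its introductory sentence indicates, and that the enzymes were assayed as planned. The point is minor. It concerns descriptive safety tables only and changes no primary or key secondary inference. It is a free improvement.

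**What to change.** Add creatine phosphokinase and MB-creatine phosphokinase to the biochemistry list in SAP 8.8.2, with the same observed-value, change-from-baseline and shift-table outputs as the other analytes. In the shift-table sentence, state that it covers every analyte in the protocol panel. If the enzymes were not assayed or were dropped on purpose, record and justify this in the SAP's section on changes from the protocol instead.

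If the values are in the database, the cost is two more parameters in existing table programs, with no new sampling. If they are not, the cost is one justified entry.

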7 STUDY INTERVENTION DISCONTINUATION AND PARTICIPANT DISCONTINUATION/WITHDRAWAL

7.1 DISCONTINUATION OF STUDY INTERVENTION

The Investigator should discontinue study intervention and specifically ensure that a participant stops taking the investigational drug if the bioanalytical results at Month 1 or Month 3 shows the following changes:

1. Confirmed 3-fold or greater elevations above the Upper Limits of Normal (ULN) of

These stopping rules for discontinuation are established based on

Discontinuation from investigational oral treatment does not mean discontinuation from the study, and remaining study procedures should be completed as indicated by the study protocol. If a clinically significant finding is identified (including, but not limited to, changes from baseline) after enrollment, the investigator or qualified designee will determine if any change in participant management is needed. Any new clinically relevant finding will be reported as an AE.

The data to be collected at the time of study intervention discontinuation will include the following:

- AE complete follow-up (if the treatment is stopped following an AE)
- Last investigational medication administration date and time

The physician can decide to re-introduce the investigational treatment if it was stopped because of a concomitant acute condition he/she considers unrelated to the treatment.

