8 STATISTICAL METHODS

8.1 General statistical conventions

All statistical procedures will be completed using SAS® version 9.3 or higher.

Unless otherwise stated, all statistical testing will be two-sided and will be performed using a significance (alpha) level of 0.05. Two-sided 95% confidence intervals (CI) will be provided for the difference between treatment groups.

Descriptive statistics (mean, standard deviation, 95% confidence interval for mean, minimum, median, maximum, and number of observations and missing cases) will be used for quantitative variables. Frequencies and percentages will be used for categorical variables. The summaries will be presented by treatment group, unless otherwise specified. Percentages will be rounded to one decimal place.

Unless stated otherwise, unscheduled data will not be included in the summaries or analysis.

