8.2 Data Listing

All subject data will be presented in individual subject data listings. Unless otherwise stated, unscheduled visit results will be included in date/time chronological order, within subject listings only. All listings will be sorted by treatment group, investigational site, subject number, date/time and visit. Subject's gender and age will be stated on each listing. Unless otherwise stated, data listings will be based on all randomized subjects.

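### No table described in the SAP counts, by treatment group, the participants who meet the visible 3 x ULN stopping criterion of protocol 7.1

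*SAP*

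**What the plan says.** **Stopping rule.** Under protocol 7.1 the investigator makes sure that the participant "stops taking the investigational drug if the bioanalytical results at Month 1 or Month 3 shows the following changes". The listed change that can be read is "Confirmed 3-fold or greater elevations above the Upper Limits of Normal (ULN) of"; the text then breaks off, so the analytes and any further items are not visible. The same section keeps the participant in the study for the remaining procedures after drug is stopped.

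**Planned laboratory outputs.** SAP 8.8.2 has three: descriptive statistics of values and changes by arm and visit, a three-category shift ("Shift tables from Baseline to the end of treatment, with regard to normal range (low, normal, high), will be presented by treatment group"), and listings. SAP 8.1 includes the maximum among the descriptive statistics.

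**Unscheduled results.** SAP 8.1 says: "Unless stated otherwise, unscheduled data will not be included in the summaries or analysis". SAP 8.8.2 states no exception. SAP 8.2 adds that "unscheduled visit results will be included in date/time chronological order, within subject listings only".

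**Extra samples.** Protocol 8.2 allows one more draw: "In case of previous abnormalities or new symptoms, a blood sample can be collected at M5". The COVID-19 part of the protocol synopsis also foresees ad hoc safety blood draws.

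**The concern.** The first general objective of this three-arm trial includes the safety of two doses. The sponsor set a numeric laboratory threshold that is serious enough to stop drug. One would expect the final tables to show how many participants per arm reached it, how often it was confirmed, and how many stopped. The SAP calls for no ULN-multiple count, no shift to the worst post-baseline value and no tabulation of who met the rule. A reader of the planned tables could not compare the two doses with placebo on this criterion without going through the listings by hand after unblinding.

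**Working it through.** The plan states no figure on this point, so there is none to reproduce. The check is to trace where a value of 3 x ULN or more would appear.

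**1. What *end of treatment* means.** SAP 8.8.2 does not say. SAP 8.7 defines a last assessment on treatment, but for the primary efficacy endpoint only. Protocol 8.2 equates the end of treatment with the M6 visit when it describes the gallbladder ultrasound. Both readings are therefore open.

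**2. Shift table, read as the M6/M9 visit.** Four constructed participants, values in multiples of ULN, with high meaning above 1:

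| Participant | Baseline | M1 or M3 | M6/M9 | Shift cell | 3 x ULN or more at any visit |
|---|---|---|---|---|---|
| A | 0.8 | 3.5 | 0.9 | normal to normal | yes |
| B | 0.8 | 1.1 | 0.9 | normal to normal | no |
| C | 0.8 | 1.0 | 1.1 | normal to high | no |
| D | 0.8 | 1.0 | 3.5 | normal to high | yes |

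A and B share a cell, and so do C and D. A is the case that the stopping rule addresses: drug is stopped early, the participant stays in the study, and the last sample is taken off drug.

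**3. Shift table, read as the last on-drug value.** If A stops on the 3.5 value, A is tabulated as normal to high. The elevation is then visible, but it is in the same cell as a last value of 1.1. Severity is lost; the shift is not.

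**4. Unscheduled samples.** A confirmed elevation implies a second determination, and the schedule of activities has no visit for one. If the repeat is entered as unscheduled, SAP 8.1 and 8.2 confine it to listings. The same holds for ad hoc draws, and for the M5 draw if M5 results are treated as unscheduled. The triggering M1 or M3 value is a scheduled sample and stays in the by-visit statistics. What leaves the tables is the confirmation, together with any elevation first seen on an extra sample. Protocol 1.3 replaces the M1 and M3 visits by telephone calls during the outbreak, so for some participants an ad hoc draw may be the only early post-baseline value.

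**5. Other outputs that could show a case.**
- By-visit maximum: shows that at least one scheduled value was high, not how many participants or whether it was confirmed.
- SAP 8.8.1, treatment-emergent events leading to discontinuation: by arm, but only if an adverse event was reported with drug discontinued as the action; it counts event terms, not threshold crossings.
- Events of special interest: falls, injurious falls and orthostatic hypotension; none is a laboratory event.
- Listings: complete, but not a count.

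**6. What a count could show (assumed rates; the documents give none).** Planned arm size is 231 / 3 = 77. The chance of at least one case in an arm is 1 - (1 - p)^77: 53.9% for p = 1%, 78.9% for 2%, 90.4% for 3% and 98.1% for 5%. These take all 77 as having post-baseline laboratory data. Real denominators will be smaller and the chances lower.

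**The case against.** The case for leaving the SAP as it is has substance.

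- Protocol 9.4.5 promises only descriptive statistics for laboratory data, so the SAP's shift table goes beyond it.
- Protocol 8.2 has the investigator review each laboratory report and judge out-of-range values, and protocol 7.1 turns clinically relevant findings into adverse events.
- Events leading to discontinuation are tabulated by arm, overall and by system organ class and preferred term, with a separate listing.
- All laboratory data are listed, sorted by treatment group, with unscheduled results included.
- The DSMB is unblinded for its reviews and sees bioanalytical data every three months (SAP 3.2, protocol 10.1.6).
- Table templates are in a separate document that is not available here.

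All of this stands, and it rules out some stronger inferences. A reader might infer that a laboratory signal would be invisible in the report; the by-visit maximum, the adverse event tables and the listings each give partial sight of it. A reader might infer that the SAP tabulates exactly the analytes in the stopping rule; with the analytes redacted, this cannot be verified. Protocol 8.2 collects creatine phosphokinase and mb-creatine phosphokinase, for example, and the SAP 8.8.2 list omits both. A reader might also infer that repeat and M5 samples are certain to drop out of all summaries; neither document states how they are classified, and M5 is a contact named in the protocol.

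None of it supplies a by-arm count of participants at the threshold. Adverse event tables depend on investigator reporting, and DSMB review protects participants during the trial rather than defining the final report.

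**Conclusion.** The point holds as a gap in the planned tables. Participants who meet the visible 3 x ULN criterion can be found only in listings, as a by-visit maximum without a participant count, or indirectly through adverse event tables. The shift table fails to isolate them under either reading of *end of treatment*: one reading can miss an early peak that resolves, and the other pools it with marginal elevations. The SAP does not contradict the protocol, and no sample size, power or alpha is affected. The size in this trial cannot be estimated, because the documents give no rate for such elevations.

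The conclusion rests on the SAP text without the table templates, on a stopping rule that is only partly visible, and, for the unscheduled samples, on an inference about how they are recorded. It is a change that should be made because it is cheap and bears on a stated objective.

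**What to change.** In SAP 8.8.2:

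1. Make the shift tables run from Baseline to the worst post-baseline on-treatment value. Include repeat, M5 and ad hoc samples as a stated exception to SAP 8.1. Keep the end-of-treatment shift as secondary, and define the end of treatment for laboratory data.
2. For each parameter named in protocol 7.1, add the number and percentage of participants per arm with any post-baseline value at or above the protocol's ULN multiple, with a confirmed one, and who stopped drug. Use participants with at least one post-baseline value as the denominator. Check that each of these parameters is on the SAP 8.8.2 list.

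The cost is SAP wording and one or two extra tables. No new data are needed, because the values are already collected and listed, and the stopping rule itself is untouched. The downside is that unscheduled samples slightly raise the apparent rate of abnormal values in participants who are tested more often; showing confirmed cases separately makes this easier to judge.
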